9.0 SUBJECT SCREENING AND INFORMED CONSENT

Screening and Enrollment

Patients referred for AVG implant should be screened for study eligibility. A member of the Research Team will evaluate the patient for eligibility. If all initial inclusion criteria are met and no exclusion criteria are present, a member of the Research Team should inform the patient about the study's purpose and should obtain written informed consent.

Final enrollment eligibility is determined at the time of surgery, after the physician has confirmed the final inclusion criterion is met. Enrolled subjects will be assigned a unique study subject identification number. Each study site will maintain subject screening and enrollment logs. Reason for screen failures will be recorded. Screening log data will not be included in the primary database but will be reviewed during study monitoring.

Baseline Imaging

Angiographic or ultrasonic imaging of the target limb vasculature is routinely performed as part of determining the optimal AV access plan for a patient. As part of screening, baseline imaging should be reviewed to determine whether the patient meets the following criteria (as determined by the physician) for use of the VIG:

- General: Flow rate must be adequate for the creation of dialysis access, as previously mapped with ultrasound or angiography
- Vein inner diameter at planned anastomosis site is 4 -7 mm in luminal diameter
- Artery inner diameter at planned anastomosis site is at least 3.5 mm in luminal diameter

Informed Consent

A member of the Research Team will approach the subject to obtain written informed consent. The background of the study and the benefits and risks of procedures and the study should be explained to the subject. The subject (or their legal representative, if applicable) must sign the consent form prior to initiation of study procedures. The consent form used must be approved by the study site's IRB. Failure to provide consent renders the subject ineligible for the study. Subjects will be given a copy of the signed informed consent document. The signed informed consent will be retained with the study records at the site. It is the responsibility of the investigator to

assure that informed consent is obtained from each subject in accordance with the guidelines of the IRB and all applicable regulatory guidelines. A sample informed consent form is provided in **Appendix B**.

10.0 STUDY PROCEDURE

General Procedure

The procedure will be performed in accordance with the VIG Instructions for Use (IFU, **Appendix A**). A commercially available 6mm diameter ePTFE graft will be used. Conventional grafts or grafts designed for early cannulation (within 24-48 hours) may be used. The study procedure will be performed in an operating room that has fluoroscopic imaging capability for guiding placement of the VIG. The anesthesia regimen will be determined at the physician's discretion; there are no study-specific anesthesia requirements. A regional nerve block is typically performed for placement of an AVG. Standard, routine hemodynamic monitoring will be performed to assess cardiovascular status throughout the procedure. Heparin anticoagulation may be provided at the physician's discretion.

Small skin incisions will be made for tunneling the graft under the skin in a standard manner. The VIG device is provided pre-loaded within a customized catheter-based delivery system for over-the-wire delivery. The VIG is inserted through an introducer sheath placed in the target vein so that the 'vessel end' of the VIG is deployed within the vein, and the 'graft end' extends out of the vein for connection to the graft. Delivery and deployment will be performed under fluoroscopic guidance. The VIG will be deployed first, connected to the AVG, then the graft and VIG will be flushed and clamped. The arterial anastomosis will then be created using a standard suturing method.

NOTE: Although not expected, if connection of the venous graft segment using the VIG is attempted but not able to be completed, the venous anastomosis should be completed using standard suturing. Such situations will be considered as an acute device failure.

Following establishment of the AV circuit, the skin incisions will be sutured closed using standard techniques. The subject will be moved to a recovery area for monitoring prior to discharge. It is anticipated that most subjects will be discharged the same day or within 24 hours following the AVG implant procedure.

Use of Clamps

To avoid mechanical damage or disruption to the AVG or VIG, surgical clamps or other tools with teeth or other sharp features should not be used during the AVG implant procedure. An atraumatic or guarded (e.g., rubber) clamp should be used for clamping the AVG, as needed. Do not clamp or manipulate the VIG with surgical tools. Use only gentle pinching with the fingers to hold the VIG and to control hemostasis.

Additional Treatment

It is anticipated that no other interventional treatments will be required during the implant procedure. At the venous anastomotic site, no further treatment should be provided if the luminal diameter is $\geq 90\%$ of the adjacent normal vessel, based on operator's assessment. If the luminal diameter is $<90\%$, balloon angioplasty may be performed as follows:

After deployment, the nitinol-reinforced VIG may be smoothed and more fully seated against the vessel wall by inflating an angioplasty balloon. Balloon treatment should be performed according to the manufacturer's instructions, by a physician skilled in peripheral vascular interventional techniques. The balloon diameter used should be equal to that of the VIG diameter and should be no larger than 6mm when used to treat the VIG segment that is within the AVG. The balloon should be inflated within the VIG along the entire length. Multiple inflations may be needed. To avoid possible displacement of the VIG, the physician should assure that the balloon is fully deflated prior to carefully removing the balloon.

Vascular Graft for Hemodialysis

Vascular grafts that meet the following requirements, as determined by the physician, may be used: commercially available, straight (not-tapered), 6 mm inner diameter ePTFE grafts. Adequate graft length and trimming must be carefully determined to facilitate optimal positioning after the venous and arterial graft anastomoses have been completed. The graft should never be too short.

Treatment of Ipsilateral Central Venous Stenosis Prior to Enrollment

Ipsilateral central venous stenosis is a study exclusion. However, a patient with central venous stenosis may be considered for the study following successful treatment of the stenosis. Central stenosis angioplasty may be performed first, then immediately followed with the study procedure. The patient may be enrolled if, as assessed by the investigator, the central stenosis has <30% residual stenosis, which is the KDOQI threshold for successful intervention. The patient should not be enrolled if the residual stenosis is $\geq 30\%$ or if the investigator determines that the treatment could impact the ability to assess the study endpoints (e.g., acute device success, graft patency, safety).

Study Device Failure, Defect, or Suspected Device Problem

Device malfunction is defined as *any occurrence in which the study device does not perform as intended, when used or attempted to be used in a study procedure*. As described in the IFU, a visual examination of the VIG should be performed at the time of opening the packaging and prior to use in a subject. Defective devices (obvious or suspected) should not be used. A replacement VIG should be obtained and the study procedure continued. A device accountability log will be used to account for all used and opened/unused devices in this study.

If a VIG defect or malfunction is discovered/suspected any time prior to vascular deployment, the VIG should not be used. A replacement device/component should be used and the study procedure continued. A Device Malfunction CRF must be completed for all device malfunctions, failures or suspected failures, and the defective product identification should be recorded on the device accountability log. Whenever possible, a defective/suspected defected VIG should be returned to the Sponsor for evaluation.

The Device Malfunction CRF should be used to report and provide details of situations in which the VIG does not perform as intended. Failure of the VIG to perform as intended may potentially be due to a variety of reasons, including defect or suspected defect in the device itself or the delivery system; operator error; anatomic issues; or other reasons. If use of the VIG is attempted but ultimately the device is not able to be used, a Device Malfunction CRF should be submitted to report the surrounding details.

NOTE: Device Malfunctions should be reported within 24 hours of discovery. 24-hour reporting of device malfunctions will assist with Sponsor's efforts to assess whether any SAEs associated with a device malfunction may also have occurred.

Bailout Procedure

Bailout procedures are not anticipated but could potentially be required if, for example, the VIG does not deploy correctly, does not seal correctly, is not deployed at an acceptable location, or if there are any major vascular events. In such cases, the subject should be referred for surgical intervention. No attempt should be made to remove an improperly deployed VIG using percutaneous methods.

Assessment of Graft Flow at the End of the Procedure

An AVG placed using the VIG and a sutured arterial anastomosis typically has a pulse and/or thrill which is easily palpable over the skin or directly on the AVG prior to closure of the surgical incisions. Thus, the AVG flow assessment is similar that used for standard sutured AVGs. An optimal method to confirm AVG patency at the end of the implant procedure is to feel a thrill near the arterial anastomosis or confirm a Doppler signal. Auscultation using a sterile or covered stethoscope is also acceptable. At the physician's discretion and as warranted, a final angiogram may also be performed to verify patency of the graft.

Initial Use of the Graft for Hemodialysis

Initial hemodialysis cannulation of AVGs placed with the VIG should be performed in accordance with the graft manufacturer's Instructions for Use. After needle withdrawal, use gentle, non-occlusive digital pressure to compress the cannulation site until hemostasis is achieved. The VIG should NOT be directly cannulated. In accordance with standard practice, once placed, AVGs should be used for hemodialysis access as soon as deemed appropriate by the nephrologist and/or operator. For standard ePTFE AVGs, the time from placement to first cannulation is typically after two weeks. Early cannulation AVGs can be used sooner, in accordance with approved labeling. Every effort should be made to minimize infection risk by removing central catheters as soon as possible.

11.0 FOLLOW-UP PROCEDURES AND GRAFT INTERVENTIONS

Subject Management

Prior to discharge, the study investigator or their designee should confirm that the subject understands the postoperative care requirements, as determined by the physician, and the required follow-up schedule. The two-week visit should be scheduled.

It is recommended that investigators follow the *Fistula First Guidelines* for vascular access monitoring (http://esrdnetwork18.org/pdfs/QI%20-%20FF%20Tools/FFTool_VAMPFlowChrt.pdf or current).

Pharmacologic Regimen

There are no study-specific pharmacologic requirements. The need for intraoperative and postoperative anticoagulation therapy should be based on subject history and maintained as deemed appropriate by the physician. Anticoagulation/anti-platelet therapy will be recorded on the eCRF.

Follow-up Evaluations

Subjects will be followed at two weeks and monthly thereafter through six months to assess AVG patency and any complications, if applicable. Measurement of access flow rate is part of standard care. Data from routine AV access flow monitoring performed as part of usual care, as available, will also be collected.

Graft ultrasound evaluation should be performed at the 3- and 6- month follow-up visits and the results recorded on the CRF.

NOTE: For reference and in accordance with standard care, baseline flow measurements are typically assessed during two dialysis sessions two weeks apart; and monthly measurements will be performed thereafter. An access flow rate < 500 mL/min or a drop in access flow rate of 25% from baseline should trigger an angiographic evaluation of the AVG and possible intervention.

Telephone Follow-up for Subjects Who Miss Final Visit

If a subject misses or is unavailable/unwilling to return for the final 6-month follow-up visit, telephone follow-up with the subject or their dialysis center should be attempted to determine the patency status of the AVG and to gather as much additional information as possible to complete the 6 month follow up and study completion CRFs. Telephone follow-up should be done only if the subject is unwilling or unable to return for an in-person visit. If the subject cannot be reached, then their dialysis center should be contacted (if allowed) to collect information about the most recent hemodialysis using the AVG. If it is not possible to reach the subject by phone or to contact the dialysis center, then the subject will be considered as lost-to-follow up.

Follow-up Considerations Related to the COVID-19 Pandemic

To reduce the likelihood of community exposure to COVID-19, investigators will be allowed to implement non-contact monthly study follow-up visits, in accordance with institutional and IRB requirements and approval to do so, and as deemed appropriate based on the COVID-19 pandemic situation at each site. Non-contact follow-up visits may include communications via telephone, FaceTime, email, Virtual Care or similar. In lieu of an in-person AVG patency assessment, investigators should obtain a copy of the most recent hemodialysis record as verification of AVG patency.

If non-contact follow-up is implemented due to the local pandemic situation, AVG ultrasound examinations will not be expected (at the 3- and 6-month follow-ups) and failure to perform the ultrasound examination will not be considered as a protocol deviation.

Investigators will be required to report the reason for performing non-contact follow up (due to pandemic, or other reason).

Graft Interventions

As per standard care following the AVG implant procedure, AVG interventions should be avoided within the first 7 post-operative days. As warranted and determined by the physician, standard balloon angioplasty and thrombectomy procedures may be performed within the AVG, VIG, and adjacent native artery and vein.

Mechanical thrombectomy devices that use spinning, rotating or other movable parts should NOT be used within the VIG, as this may result in entanglement or other damage to the VIG. The balloon diameter used should be equal to that of the VIG diameter and should be no larger than 6mm when used to treat the VIG segment that is within the AVG.

Summary of Tests and Procedures

The required schedule for subject treatment and follow-up evaluation is shown in **Table 1**.

Table 1: Schedule of Subject Treatment and Evaluation

Timeframe (window)	Test/Procedure
Pre-procedure (within 30 days)	Baseline imaging of target AVG site (performed as part of standard care) Baseline labs: Hgb, Hct, WBC, platelets
Pre-procedure (within 24 hours)	Urine pregnancy test for female subjects with reproductive potential
Immediately following end of AVG implant procedure (before leaving surgery suite)	Confirmation of AVG flow (palpable thrill/pulse, audible bruit) At the physician's discretion and if warranted, an angiogram may also be performed to confirm patency.
Post- procedure (within 48 hours)	Post procedure labs: Hgb, Hct
At discharge	Confirmation of AVG flow (palpable thrill/pulse, audible bruit)
2 weeks following the procedure (14 +4/-7 days)	Clinical follow- up with AVG evaluation (includes collection of information regarding any subsequent hospitalization, AEs, AVG interventions)
30, 60, 90, 120, 150,180 days following the procedure (± 14 days)	Clinical follow- up with AVG evaluation (includes collection of information regarding any subsequent hospitalization, AEs, AVG interventions) AVG flow rate evaluation (ultrasound or similar) is performed at the 90-day and 180-day follow-up visits.

Final Events

The following final events will justify cessation of study follow-up: death, AVG abandonment, lost to follow up (at least 3 attempts to contact the subject should be made and documented), or completion of study follow-up.

12.0 POTENTIAL RISKS

Potential adverse events that may occur and/or require treatment with use of the VIG include but are not limited to:

- allergic reaction to device materials or procedure medications
- anastomotic disruption or tearing
- aneurysm
- artery tear or rupture
- bleeding
- bruising
- contrast dye reaction
- death
- device breakage
- dissection or 'tissue flap' in blood vessels in which the VIG has been inserted

- embolism
- hematoma
- infection
- inflammation
- kinking/compression of the AVG and/or VIG device
- migration or misplacement of VIG device
- occlusion
- pseudoaneurysm in the AVG, VIG device, or adjacent native blood vessels
- seroma
- stenosis of the AVG
- swelling of implanted arm
- thrombosis of the AVG
- vessel spasm

Many of the potential AEs listed above are similar AEs that may occur during and after AVG placement using standard surgical techniques. Potential risks of a standard surgical procedure to implant an AVG for hemodialysis include but are not limited to the following:

- failure of sutures
- bleeding immediately after the procedure
- infection
- possible need for re-operation

The VIG will be used with a standard 6 mm AVG for hemodialysis that is sold and packaged separately. Potential AEs that may occur with use of the AVG are described in the Instructions for Use packaged with the AVG.

Pregnant subjects are excluded from the study. In females of reproductive capacity, a pregnancy test must be performed prior to the procedure. This is to ensure that a fetus is not irradiated. Other potential risks to a fetus related to the study procedure are unknown.

There are no unique blood tests required for the study; however, results of standard blood tests performed to evaluate general health status at baseline, during the study procedure and during study follow-up will be included with the study data. Risks of having blood drawn include infection (rare) and bleeding (rare).

Steps to Minimize Risk

The following steps will be taken to minimize potential risks:

- The study will include only investigators who have prior training and clinical experience using the VIG.
- The study procedure will be performed in a surgical suite with radiologic imaging capabilities. If the study procedure is unable to be performed (not expected), the patient will be able to receive traditional surgical graft implantation.

13.0 POTENTIAL BENEFITS

Potential clinical benefit for the VIG is unknown. Anastomoses with the VIG may potentially reduce venous vessel trauma, improve the local vessel wall shear stresses, and promote laminar flow, thereby improving patency.

14.0 SUBJECT WITHDRAWAL FROM THE STUDY

Subjects may withdraw consent from the study at any time. Study data collected prior to withdrawal will be analyzed and included with the final study results. The investigator may withdraw the subject from the study at any time if assessed to be in the best interest of the subject.

15.0 CRITERIA FOR STUDY TERMINATION

The study may be terminated at any time for reasons of safety, based on a recommendation by the IRB, the study Clinical Events Committee (CEC), or other considerations of the Sponsor. Serious, device-related or possibly related AEs that are unexpected in either frequency or type may prompt a review by the principal investigator, CEC, and/or Sponsor, and may lead to consideration of stopping the study. Such a review and discussion will be documented and included with the study records.

16.0 STUDY DURATION

Enrollment is expected to occur over a 6-month period. Thus, completion of enrollment and 6-month follow up is anticipated within a 12-month duration.

17.0 TRAINING

Training of appropriate clinical site personnel will be the responsibility of the Sponsor or their designees. To assure uniform data collection and protocol compliance, trainers will provide an educational session to review the VIG-CAS Investigational Plan, techniques for the identification of eligible subjects, instructions on data collection, follow-up schedules and regulatory requirements. Ongoing email and telephone feedback regarding completion of eCRFs will be provided by the DCC and study monitors.

Prior to enrollment start, refresher technical training for set-up and use of the VIG will be provided. Only prior investigators with experience using the VIG will participate in the study; thus, roll-in cases will not be required.

18.0 STATISTICAL ANALYSIS

All subjects who meet the enrollment criteria and in whom use of the VIG is attempted will be included in the intention-to-treat analysis population.

Descriptive statistics will be used to summarize subject baseline and outcome data. Continuous variables will be summarized using means, standard deviations, medians, interquartile ranges, minimum and maximum values. Categorical variables will be summarized in frequency distributions. A copy of the database used to prepare clinical report summaries will be archived to enable any statistical analyses performed to be replicated. A full data listing will be prepared at the completion of the study. Listings of data represented on the CRF will include key

baseline, demographic, and outcome variables to facilitate further investigation of tabulated values and to allow for clinical review of safety variables.

No formal hypotheses will be tested or associated significance levels assigned to study results. Nominal confidence intervals may be calculated in summarizing clinical results for study endpoints but not for purposes of product labeling.

In addition to summarizing and reporting SAEs that are part of Study Endpoint #6, listings of other AEs (serious and non-serious) will be prepared and evaluated.

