24.0 MEASURES TO AVOID BIAS

Measures that will be used to avoid bias include:

- Use of independent CEC
- Objective criteria for endpoint determination
- Intention-to-treat primary analysis

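### Must Section 18 state how early exits with a patent graft, and subjects never cannulated, are counted in the patency and cannulation endpoints?

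*Combined protocol and SAP*

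**What the plan says.** Section 18.0 of the combined protocol and SAP states that "Descriptive statistics will be used to summarize subject baseline and outcome data". For categorical data, "Categorical variables will be summarized in frequency distributions"; for continuous data, "Continuous variables will be summarized using means, standard deviations, medians, interquartile ranges, minimum and maximum values". Eligible subjects in whom the device is attempted "will be included in the intention-to-treat analysis population", and Section 24.0 lists "Intention-to-treat primary analysis" among its measures against bias.

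The same section limits what the results are for: "No formal hypotheses will be tested or associated significance levels assigned to study results", and "Nominal confidence intervals may be calculated in summarizing clinical results for study endpoints but not for purposes of product labeling". It adds that "A full data listing will be prepared at the completion of the study", and that the database behind the report will be archived so that analyses can be replicated.

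Section 8.0 defines Endpoints #1 and #3 as percentages of subjects free from an event, and Endpoint #4 as the time from placement to first cannulation. Under Final Events in Section 11.0, death and loss to follow-up end follow-up. Section 14.0 keeps data collected before a withdrawal in the analysis. Kaplan-Meier is named only in Section 2.0, in the account of the completed pivotal study. Sections 2.0 and 6.0 carry over that study's population, schedule and endpoints, but do not mention its analysis method.

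**The concern.** An intention-to-treat population fixes who is counted, not what status they receive. A subject who dies on day 60 with a working graft has had no loss of access, yet cannot be assessed at 6 months. A crude percentage could treat that subject as patent, as failed or as absent, and the choice would be made after outcomes are known in an open-label, single-arm study. One subject in 15 is 6.7 percentage points.

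For Endpoint #4, a mean or median exists only for subjects who were cannulated, so those who never reach cannulation drop out of the summary and the remaining times look shorter. If the rule were chosen to flatter the result, the additional effectiveness data that Section 5.0 says the study will collect would not be on the same footing as the pivotal study's Kaplan-Meier figures.

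**Working it through.** The plan gives no design figure to reproduce: no power, significance level or derived sample size.

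**Step 1: which rules the text leaves open.**
- *Dropped:* Section 18.0 puts every eligible subject with an attempted device in the analysis population, and Section 14.0 retains pre-withdrawal data. Both tell against it.
- *Failed:* Endpoints #1 and #3 count freedom from a named event. A subject who exits with a patent graft has had none. The definitions tell against it.
- *Event-free or censored:* both remain open.

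Section 11.0 also shrinks the number of open cases. Patency status is sought from the subject by telephone, then from the dialysis center, and during non-contact follow-up from the hemodialysis record.

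**Step 2: average size.** Inputs: n = 15 (Section 6.0). For Endpoint #3, S = 0.6021 at 180 days (Section 2.0). For Endpoint #1, Section 2.0 gives only a lower confidence bound of 86.98%, so S = 0.90 is assumed, with range 0.87 to 0.93. Also assumed: k = 1 or 2 subjects with exit times uniform over 180 days and unrelated to graft status, and exponential time to event.

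- Event-free: [(15 − k)S + k(1 − S)/(−ln S)]/15
- Failed: (15 − k)S/15

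The factor (1 − S)/(−ln S) is 0.9491 at S = 0.90 and 0.7843 at S = 0.6021. For k = 1, S = 0.90: (14 × 0.90 + 0.9491)/15 = 90.3%. For k = 2, S = 0.6021: (13 × 0.6021 + 2 × 0.7843)/15 = 62.6%. The dropped and Kaplan-Meier columns come from simulation (100,000 trials).

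| Endpoint | k | Event-free | Dropped | Failed | Kaplan-Meier | SD (points) |
|---|---|---|---|---|---|---|
| #1, S = 90% | 1 | 90.3 | 89.7 | 84.0 | 90.0 | about 8 |
| #1, S = 90% | 2 | 90.7 | 89.3 | 78.0 | 90.0 | about 8 |
| #3, S = 60.21% | 1 | 61.4 | 59.3 | 56.2 | 60.2 | about 13 |
| #3, S = 60.21% | 2 | 62.6 | 58.4 | 52.2 | 60.2 | about 13 |

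Over S = 0.87 to 0.93, event-free exceeds S by 0.2 to 0.9 points for Endpoint #1. For Endpoint #3 the excess is 1.2 points (k = 1) and 2.4 points (k = 2). Only scoring exits as failures moves the figures by 4 to 12 points, and the definitions tell against that.

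**Step 3: a single data set.** Averages can hide a bad ordering of dates. With two exits and one graft loss, event-free gives 14/15 = 93.3%; Kaplan-Meier lies between 12/13 = 92.3% and 93.3%. With two exits and six Endpoint #3 events, event-free gives 9/15 = 60.0%; Kaplan-Meier lies between 7/13 = 53.8% and 60.0%. The largest gap, 6.2 points, needs both exits to precede every event. The exact 95% interval for 9/15 is 32.3% to 83.7%.

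**Step 4: Endpoint #4.** Assumed data: 13 subjects cannulated on days 14, 14, 15, 15, 16, 17, 18, 20, 21, 22, 25, 28 and 30, and two never. Among the 13, the mean is 255/13 = 19.6 days and the median 18. Keeping all 15, the median is the eighth value, 20 days. The shift is two days, and 13 of 15 cannulated would be plain from the listing.

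**The case for a change.** The best case for a change is that exits are plausible and a rule is cheap. At the pivotal death rate of 4/158, the chance of at least one death among 15 subjects is 1 − (154/158)^15 = 32%, before withdrawals and losses, whose rates are not given. In the first-in-human study (Section 4.0), 3 of 9 subjects left early: dropping them gives 6/6 patent, while failing them gives 6/9. A listing permits a recount but does not say which figure the report should carry. That much stands. The 32% is an upper bound on an open case, however, because a death matters only if the subject was event-free beforehand.

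A further open case is a graft excised for infection with no earlier thrombosis or patency procedure. It is a loss for Endpoint #1, but the wording of Endpoint #3 does not name it. Read literally, one such subject would give 14/15 = 93.3% for cumulative patency and 15/15 for primary patency. An analyst would see that a lost graft cannot keep its primary patency.

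It does not stand that a crude percentage is biased however exits are counted. For death with a working graft, counting the subject as event-free validly estimates one minus the cumulative incidence of access loss. Censoring the death estimates patency as if deaths did not occur. These are different targets, and statisticians differ over which to report. Requiring Kaplan-Meier at day 180 would also raise its own question: the final visit may fall from day 166 (180 − 14), so some completers would have no documented status at day 180.

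**Conclusion.** Section 18.0 leaves out a counting detail, but no change to the plan follows. Read with the population definition, Section 14.0 and the endpoint definitions, it leaves a choice between event-free and censored. On average that choice is worth under 1 point for Endpoint #1 and about 1 to 2.4 points for Endpoint #3, well inside sampling error at n = 15. These sizes assume one or two exits unrelated to graft status, a constant event rate, 87% to 93% cumulative patency and the pivotal 60.21% for primary patency. More exits, or exits linked to a failing graft, would widen them.

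No test, planned comparison or label claim depends on the result. Analysts working on endpoints that the pivotal study reported by Kaplan-Meier can be expected to handle early exits sensibly and to show how many subjects left early or were never cannulated. The listing and archived database let anyone apply another rule. A sentence in the clinical report giving those counts and the rule used would serve as well as an amended Section 18.0.
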